6.3 Study Product Use and Reporting

Subjects will never be forced to smoke or use any study product.

All subjects will smoke their usual brand cigarette according to their usual smoking behaviors through check-in of Test Visit 1 and will be instructed to follow their randomization arm assignments through discharge from the study. However, subjects will be instructed to report use of any other tobacco- or nicotine-containing products.

Each day from Day 3 through discharge from the study on Day 57, subjects randomized to the *my*bluTM arm will report the number of pods started, whether they took more than 50 puffs from the *my*bluTM product, and the number of cigarettes smoked. Subjects randomized to the continue-smoking arm will report the number of cigarettes smoked each day from Day 3 through discharge from the study. Subject self-report will be via a text-message system.

Subjects will be instructed to report product failures to the clinic staff (to be documented by the clinic staff) and to temporarily stop use if they experience any signs of nicotine toxicity (such occurrences will be reported to the clinic staff and documented as AEs).

6.3.1 Confinement Periods

Areas dedicated to product use (within the clinic or outdoors) during the confinement periods must be in accordance with applicable state and local regulations governing the facility. All applicable regulations regarding indoor and outdoor smoking/study product use must be understood and followed by the Investigator.

Dedicated space for use by product type (e-cigarette or combustible cigarette) during product use will be identified to minimize the potential for cross-contamination and illicit study product use. The subjects using an e-cigarette product should not have access to areas where smoking is allowed, and should not share confined sleeping quarters. If necessary, the clinic may schedule the study arms to be confined on separate days to alleviate these concerns.

The clinic staff will provide a demonstration and training of the proper use and care of the mybluTM and JUUL[®] products before use by subjects in those respective arms, and subjects will demonstrate an understanding of the instructions. During the product training on the mybluTM product, subjects may sample each e-liquid if they choose to do so.

Generally, study product use will be *ad libitum* upon request to the staff following check-in through 23:00, except during certain events or as otherwise noted. All product use during the confinement periods will be documented by the clinic staff (i.e., each product check-out and return).

Use of products during the PK product use sessions are described in Section 6.7.1.

mybluTM Product Use

Subjects randomized to the *my*bluTM arm will turn over all cigarettes to the clinic staff upon check-in on Day -2 and will smoke their usual brand cigarettes through 23:00 on Day -1. On the morning of Day 1, they will begin participation in a 3-day in-clinic product acclimation period through the evening of Day 3. The acclimation period will afford the subjects the opportunity to try each of the four *my*bluTM e-liquids in order to become accustomed to their use and to determine those that they would be willing to use during the study. Following product training on Day 1, subjects will use each of the four products individually for approximately 2 hours each, with the order of use selected by the subject. However, only one e-liquid may be used during each 2-hour period to ensure that subjects have an adequate time to try each. Following the last 2-hour period, subjects may choose any of the e-liquids freely through 23:00 on Day 2.

At 20:00 on Day 2, subjects will complete the mybluTM Product Preference Questionnaire (Appendix 2). Subjects will rank in the order of preference those products that they would be willing to use through the end of the study. It should be emphasized that they should only rank those products that they would be willing to use. Initial product assignment for each subject will be made by the clinic staff based on preference. Beginning on the morning of Day 3, subjects will use the assigned e-liquid through Day 28.

Subjects participating in the PK sub-study will continue to use the assigned product through the evening of Day 4. New pods will be issued for use during the 24-hour urine collection from the afternoon of Day 3 to Day 4. All pods used during the 24-hour urine collections will be weighed within 24 hours before and after use, with the weights documented. A new pod will be provided after completion of the urine collection.

Upon presentation to the clinic for Test Visits 3 and 5, subjects will turn over to the clinic staff the mybluTM device. Prior to the start of the urine collection, subjects may use the same pod as was being used prior to presenting to the clinic and new pods will be issued for use during the 24-hour urine collection. All pods used during the 24-hour urine collections will be weighed within 24 hours before and after use, with the weights documented. A new pod may be used after completion of the urine collection if time allows for product use prior to discharge from the test visit.

To further improve compliance through Day 56, during the Day 28 visit subjects using a mybluTM product may be allowed to choose to switch to the alternate nicotine strength of their current flavor, to switch to the alternate flavor with the same nicotine strength as their initial choice, or to continue using the same e-liquid selected initially. Subjects will be allowed a brief trial with the alternate products if desired. The site staff will document this use, but subjects will not need to report these as a part of their product use reporting.

Usual Brand Cigarette Use

Subjects randomized to the continue-smoking arm will smoke their usual brand cigarettes throughout each confinement visit. Subjects will turn-over all cigarettes upon check-in to each test visit.

JUUL[®] Product Use

Subjects in the JUUL[®] arm will begin using the product following the demonstration and training on Day -2 and will continue to use the product through 23:00 on Day -1. Subjects in the JUUL[®] arm will not be allowed to smoke at any time from the time of check-in on Day -2 through discharge on Day 1.

6.3.2 Ambulatory Periods

Study product use according to the randomization will be *ad libitum* during the ambulatory periods according to the subject's usual smoking or e-cigarette use behaviors. Subjects are to follow the product use requirements of their respective randomization arm.

6.3.3 Product Use Compliance

Subject compliance with study product use and reporting is a critical component of this study, though 100% compliance from all subjects is an unrealistic expectation. Subjects in the *my*bluTM arm will be reminded at each dispensing for ambulatory use that they are expected to exclusively use the test products without dual use of combustible cigarettes, but that they should be honest about smoking combustible cigarettes as the laboratory assessments will detect use of these products.

Subject self-reported product use will be used as a measure of compliance. The clinic staff will monitor the frequency with which subjects complete the daily product use entries leading up to each Test Visits 2 through 5 and will discuss with subjects any concerns about the entries (e.g., missed reporting, significantly abnormal product use entries). Subjects who complete the daily product use entries on less than 70% of the study days prior to a test visit will be reminded of the importance of documenting product use. Subjects who continue to regularly fail to complete the daily product use entries may be identified by the Investigator as individuals whose noncompliance may jeopardize the integrity of the study data. Disqualification for noncompliance with these product use requirements may only occur in consultation with the Sponsor.

As solely relying on self-reported product use may lead to a conclusion of a higher rate of compliance than actually occurred, biochemical verification of compliance will also be used. While it is recognized that there are many other potential sources of CO and nicotine exposure, exhaled CO and urine cotinine will be used as methods of verifying compliance in real-time. Subjects with values inconsistent with their randomization arm (i.e., subjects in the *my*bluTM arm with exhaled CO values > 8 ppm or negative urine cotinine tests, subjects in the continue-smoking arm with exhaled CO values < 10 ppm or negative urine cotinine tests) will be questioned regarding their recent product use and any information provided will be documented in the subject file. Subjects will be reminded of the importance of compliance

with study instructions, including accurate reporting of other nicotine and tobacco products used.

NNAL is a tobacco-specific nitrosamine with a longer half-life than CO, thus may provide an estimate of compliance over a long period of time by comparison of the post-baseline values to the baseline values. As this will be measured in a bioanalytical assay, real-time monitoring will not be possible and the verification will be completed at the end of the study.

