3. SUMMARY OF STUDY DESIGN

3.1 Design and Procedures

This will be an open-label, partially-randomized, parallel-arm, multi-site study in healthy adult smokers, consisting of the main study and a PK sub-study.

The main study will assess BoE, BoPH, physiologic effects, and subjective effects with use of *my*bluTM e-cigarettes relative to continuing to smoke combustible cigarettes. To account for potential attrition, up to 175 subjects are planned to be randomized into the *my*bluTM arm (with approximately 43 subjects intended to be assigned to each *my*bluTM e-liquid) and up to 40 subjects will be randomized into the continue-smoking arm. Baseline study assessments will be made during use of subjects' usual brand combustible cigarettes during the initial test visit through the morning of Day 1. All subjects in the *my*bluTM and continue-smoking arms will return to the clinic site for test visits scheduled to occur on Days 14, 28, 42, and 56 for post-baseline study assessments, compliance checks, and product dispensing and return. The subset of subjects participating in the PK sub-study (described below) will also complete selected biomarker assessments (NNAL, NNN, 3-HPMA, CEMA, HMPMA, S-PMA, nicotine equivalents) on Days 3 and 4.

Subjects randomized to the *my*bluTM arm will participate in an in-clinic product acclimation period from Days 1 to 3. The acclimation period will afford the subjects the opportunity to try each of the four *my*bluTM e-liquids in order to become accustomed to their use and to determine those that they would be willing to use during the study. Initial product assignment for each subject will be based on preference as a method to enhance compliance. To further improve compliance through Day 56, at the end of Test Visit 3, subjects using a *my*bluTM

product may be allowed to choose to switch to the alternate nicotine strength of their current flavor, to switch to the alternate flavor with the same nicotine strength as their initial choice, or to continue using the same e-liquid selected initially. This method for initial flavor assignment and the opportunity to re-select after 28 days of use is based on natural experimentation that consumers experience when choosing an e-cigarette flavor.

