4.4 Subject Early Discontinuation or Withdrawal

Subjects will be advised that they are free to withdraw from the study at any time. In addition, subject participation in this study may be discontinued for any of the following reasons:

- AEs
- Lost to follow-up
- Non-compliance with study procedures
- Protocol violations
- Study terminated by Sponsor, US FDA, or other regulatory authorities
- Withdrawal of consent
- Investigator's discretion, including a severe laboratory abnormality or other medical condition that indicates to the Investigator that continued participation is not in the best interest of the subject

Protocol deviations/violations should not lead to subject withdrawal unless they indicate a significant risk to the subject's safety or jeopardize the scientific integrity of the study.

If premature withdrawal from the study occurs for any reason, the Investigator must determine the primary reason and record this information in the electronic case report form (eCRF). Additionally, subjects withdrawing after first use of study product according to the randomization requirements will undergo all discharge safety procedures as feasible and as

deemed necessary by the Investigator and will be contacted approximately 14 days after early termination to determine if any AE has occurred since the last study visit.

A subject withdrawn from the study due to any AE or clinically significant abnormal laboratory test values will be evaluated by the Investigator or other monitoring physician and will be treated and/or followed up until the symptoms or values return to normal or acceptable levels, or until lost to follow-up, as appropriate in the opinion of the Investigator.

If a subject becomes lost to follow-up, a reasonable effort will be made to contact the subject and perform the end-of-study safety procedures noted in the Study Events tables. A reasonable effort is considered, at minimum, two attempts via telephone (at least 1 day apart) followed by a certified letter to the subject's last known address requesting their return to the clinic site for a safety evaluation and return of any study products.

Subjects withdrawing or removed from this study cannot re-enter.

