4.6 Replacement Subjects

Subjects withdrawn or removed from the study may be replaced at the discretion of the Sponsor in order to better ensure that the intended subject completion target is reached. If replacement subjects are used, the replacement should be made with subjects matching the sex, age class, and race of the subject being replaced, if possible. Replacement subjects will be assigned a randomization number 100 higher than the subject being replaced.

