7.1 Sample Size Estimation

This study is prospectively powered to find significant decreases in the primary BoE in subjects who switch to my bluTM e-cigarettes for 28 days.

Exclusive use of blu products during a 5-day in-clinic period was previously shown to reduce the primary BoE to be assessed in this study by $\sim 60\%$ to $\sim 95\%$ (O²Connell et al., 2016). In the same study, reducing cigarette consumption by $\sim 30\%$ of that during the baseline period resulted in $\sim 13\%$ to $\sim 27\%$ reductions. However, no published data are available for the current test products, or similar e-cigarette products, over a longer use period from which a sample size may be estimated for this study. Therefore, the sample size estimation was made using Day 30 data from FDA Center of Tobacco Products Docket # FDA-2017-D-3001 (study ZRHM-REXA-08-US) where the applicant assessed similar BoE in subjects who switched to a tobacco heating product or continued to smoke combustible cigarettes during an out-of-clinic product use period.

Based on this previous data, a minimum of 29 subjects per cohort is estimated to be needed to find differences in the Day 28 S-PMA change-from-baseline value equivalent to a 50% reduction in biomarker value compared to the continue-smoking arm using one-sided significance level of 0.0125 (alpha of 0.05 adjusted for multiple comparisons using the Bonferroni method) with a power of at least 80%. Approximately 43 subjects are planned to be randomized into each *my*bluTM e-liquid cohort and 40 subjects into the continue-smoking arm to better ensure that the minimum number complete the Day 28 assessments. The following table provides the power estimate for each of the primary endpoint biomarkers assuming 29 subjects in the ITT population complete the study.

	Test group	Test group	Control group	
	baseline	change-from-baseline	change-from-baseline	
Biomarker	value	SD	SD	Power
COHb (% sat)	6.95	2.28	1.73	>0.9999
NNAL (ng)	340	178	133	0.9623
3-HPMA (µg)	1325	494	500	0.9968
S-PMA (ng)	3348	2370	1512	0.8106

The baseline and change-from-baseline SD values in this table were derived from study ZRHM-REXA-08-US in US FDA Center of Tobacco Products Docket # FDA-2017-D-3001 who had reported Baseline and Day 30 measurements for the listed biomarkers.

Abbreviations: 3-HPMA = 3-hydroxypropylmercapturic acid, COHb = carboxyhemoglobin, NNAL = 4-(methylnitrosamino)-1-(3-pyridyl)-1-butanol, SD = standard deviation, S-PMA = S-phenyl mercapturic acid.

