7.2.2 Intent-to-Treat Population

The ITT population will consist of randomized subjects with at least one documented product-use experience from Day 1, irrespective of their compliance of the product-use to which they were randomized.

7.2.3 **Per-Protocol Population**

The PP population is a subset of the ITT population who meet the requirements below. Separate populations for Product Use Periods 1 and 2 will be established based on data collected during each of those periods.

*my*bluTM and continue-smoking arms

- Have no protocol deviations significantly impacting the integrity of the analysis or interpretation of the individual endpoint under consideration (e.g., compromised urine samples, use of prohibited medications impacting the endpoint)
- Have a daily product use response rate of at least 70% during the product use period
- Have a positive urine cotinine test at each scheduled assessment

mybluTM arm

- Self-report reducing cigarette consumption by at least 90% of that reported at baseline
- Have exhaled CO values ≤ 8 ppm at each scheduled post-baseline assessment
- Have post-baseline urine NNAL values reduced by \geq 75% from baseline

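### Persistent diary non-reporters can be disqualified by open-label judgement and replaced, and no later biomarker sample is required of them, so their values drop out of the ITT analysis

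*Protocol*

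**What the plan says.** The trial is an "open-label, partially-randomized, parallel-arm, multi-site study in healthy adult smokers". Both main-study arms report product use daily by text message (Protocol 6.3).

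Under Protocol 6.3.3, staff look at reporting frequency ahead of Test Visits 2 to 5, and anyone below 70% is reminded. Those who keep failing to report may be identified by the investigator as a threat to data integrity. The section then says: "Disqualification for noncompliance with these product use requirements may only occur in consultation with the Sponsor". It gives no number at which disqualification applies.

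Three other provisions bear on this:

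- Protocol 4.4 lists "Non-compliance with study procedures" among the reasons for ending participation. It also says that deviations should not lead to withdrawal unless safety or scientific integrity is at stake. After withdrawal it asks for discharge safety procedures, and removed subjects cannot come back.
- Protocol 4.6: "Subjects withdrawn or removed from the study may be replaced at the discretion of the Sponsor".
- Protocol 7.2.3 and SAP 4.1.3 already set a diary condition for the PP population, in both arms: "Have a daily product use response rate of at least 70% during the product use period".

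The ITT population (Protocol 7.2.2, SAP 4.1.2) holds every randomized subject with one documented product use from Day 1, whatever their compliance. It is the primary analysis population.

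**The concern.** The ITT analysis is there to show what happens when smokers are offered the product and have free access to cigarettes; Protocol 3.2 gives this as the reason for the long ambulatory phase. Removal for missed texts makes a subject's outcome missing by decision. The decision is made by people who know the arm, the self-reports and the exhaled CO readings.

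If subjects who stop reporting are more often those who went on smoking, their removal from a myblu cohort would raise that cohort's mean reduction. Removing a control subject who smokes as assigned should move the control mean little, so applying the rule to both arms would not by itself cancel the effect. Removal also does little for the analysis, because the PP rule already deals with sparse diaries.

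**Working it through.** **1. What happens to the value.** Three places have to be read together.

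- Protocol 4.4 requires safety procedures after withdrawal. In Table 2 the early-termination footnote (4) appears on items such as vital signs, ECG and clinical chemistry. It does not appear on the 24-hour urine row or the BoE blood (COHb) row.
- The model in SAP 6.7.1 has change from baseline as the response, with arm, day and their interaction fixed and subject random. Baseline enters only by subtraction, and no missing-data method is stated for the primary biomarkers. A subject with neither a Day 28 nor a Day 56 value contributes nothing. (PK sub-study subjects have Day 3 to 4 values for some biomarkers, but the SAP's ITT comparison shell lists Days 28 and 56 only.)
- The shell's n is the number of observations used, not the ITT headcount.

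**2. When it can happen.** The first reporting check is at Test Visit 2 (Day 14 ± 2). A reminder comes first, and continued failure must follow. Test Visit 3 (Day 28 ± 2) collects the primary samples. The window is therefore nominally 28 − 14 = 14 days, with extremes of 26 − 16 = 10 and 30 − 12 = 18. Removal after Test Visit 3 leaves Day 28 intact and costs only Day 56. There the Day 28 value stays in the mixed model and carries some information.

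**3. The plan's own figure.** Protocol 7.1 assumes an effect "equivalent to a 50% reduction in biomarker value compared to the continue-smoking arm" at one-sided alpha 0.0125 with 29 per group. The limiting row is "S-PMA (ng) 3348 2370 1512 0.8106".

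- Difference: 0.5 × 3348 = 1674 ng.
- Standard error: √((2370² + 1512²)/29) = √(7,903,044/29) = 522.0.
- Noncentrality: 1674/522.0 = 3.207, with Welch df about 47.6.
- Power from the noncentral t: **0.8106**, as stated. With n = 28 it is 0.7946, so 29 is the minimum.

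The plan leaves room for 43 − 29 = 14 losses per myblu cohort (32.6%) and 40 − 29 = 11 in the control arm (27.5%). A few disqualifications would not break the sample size; the question is bias.

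**4. Worst-case size.** Suppose a fraction p of a cohort is removed before Day 28, all with zero reduction, and all would otherwise have given samples. The mean reduction in those left is the true mean times 1/(1 − p). The fractions are assumptions.

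| p | subjects of 43 | factor |
|---|---|---|
| 5% | about 2 | 1.05 |
| 10% | about 4 | 1.11 |
| 15% | about 6 | 1.18 |

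For example, a true 45% reduction would show as 45/0.90 = 50% at p = 10%.

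**5. A mixture illustration.** Assume that a share f of a cohort keeps smoking with no reduction, that switchers fall by R, and that a share q of the continuing smokers is removed. Then p = fq and the apparent reduction is (1 − f)R / (1 − fq). Protocol 7.1 cites reductions of about 60% to 95% under exclusive use, which gives a range for R; f and q are assumed.

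- R = 75%, f = 30%, q = 50%: 0.525/0.85 = 61.8%, against 52.5% with nobody removed. Nominal S-PMA power at n = 29, with the stated SDs held fixed, goes from 0.850 to 0.947.
- With q = 50%, over R 60–95% and f 20–40%, the rise runs from 5.3 points (48.0% to 53.3%) to 14.2 points (57.0% to 71.2%).
- If missed texts are unrelated to smoking, the shift is **0**.

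**The case against.** The strongest reply is that smoking is not the trigger. Protocol 4.3.3 says that use of other products will not necessarily end participation and does not record ambulatory smoking in the myblu arm as a deviation. Exhaled CO above 8 ppm leads only to questioning and a reminder. The trigger is missed reporting, and it applies to both arms. The sentence in 6.3.3 is also a restriction, a reminder precedes it, and 4.4 discourages withdrawal for deviations. All of this stands. It narrows the route but leaves it to judgement, since the integrity ground in 6.3.3 closely resembles the exception in 4.4.

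It can also be said that disqualification is undefined, and that equating it with removal under 4.4 and 4.6 is a reading. That is fair; it is the natural reading, and the text should settle it. Daily self-reported use is itself a secondary endpoint, so the sponsor has a legitimate interest in diary completion, but removal does not recover the missing entries.

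Three stronger readings are tempting, and the documents do not support them:

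- A reader might infer that likely smokers are taken out of the ITT population. They remain in it by definition; only the value is lost. No text links missed messages to smoking.
- A reader might infer that replacement conceals the loss. The withdrawal reason goes in the eCRF (4.4), and SAP 7.1 and Table 14.1.1 tabulate discontinuations with reasons. Replacements carry a number 100 above the subject replaced (4.6), and each comparison prints its n. Replacement restores the completer count but not the lost values.
- A reader might infer that every primary biomarker reduction is inflated. That follows only under the assumptions in the working.

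**Conclusion.** The point holds in limited form. The protocol permits a discretionary, unblinded route to missing primary data, with no threshold and no requirement to collect the outcome afterwards. The primary population is meant to be indifferent to compliance, and the PP rule already handles sparse diaries. For the Day 28 primary endpoint the exposure is about two weeks; for the Day 56 comparison of the same biomarkers, a secondary objective, it is the whole of Period 2.

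Neither the size nor the direction of any bias can be derived from the documents. The factor 1/(1 − p) is an upper case that needs every removed subject to have had no reduction and to have been willing to give samples. For Day 56 it is only a rough guide, because the Day 28 values stay in the model. The lower case is zero. The planned 29 per cohort and the stated power are not in dispute. The change is worth making because it is cheap and closes an avoidable gap.

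**What to change.** In Protocol 6.3.3 and 4.4, state that failure to complete diary entries is not on its own a reason to end participation. Keep these subjects in follow-up and collect the scheduled Day 28 and Day 56 blood and urine. Analyse them in ITT, and leave them out of PP only under the existing 70% rule. In 4.6, state that they are not replaced for this reason.

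Keep the change to diary non-reporting. Removal for safety, voluntary withdrawal, and product misuse or repeated disposal (Protocol 5.2 and 5.5) are separate matters and stay as they are.

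The cost is a short protocol amendment and a few subjects with sparse diary data who remain in follow-up. The samples are already scheduled. Keeping subjects enrolled does not guarantee that they attend, but it means that the plan itself no longer causes the loss.
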